Clonidine may produce somnolence or hypotension. Clonazepam commonly may produce somnolence. The procedure is contraindicated in patients with unstable medical problems or histories of hypersensitivity to any of the medications used, and these are exclusions in the proposed study. The procedure is conducted in the outpatient setting that permits monitoring of patients for up to 8 hours daily to permit close monitoring of vital signs and mental status.

Pregnancy

Buprenorphine and naltrexone are Pregnancy category C agents, although the safety of buprenorphine in pregnancy has been supported in clinical trials (Jones et al., 2010). Female participants will be required to use adequate methods of birth control (condom with spermicide, diaphragm with spermicide, birth control pills) to be included in the study and will be strongly encouraged to use more effective methods like a subdermal implant, IUD, or a depot contraceptive injection. Serum pregnancy tests will be evaluated at baseline and urine for pregnancy will be tested as clinically indicated during treatment according to standard clinical procedures. If a female patient does become pregnant she will be withdrawn from study medication and offered continuing treatment with methadone or buprenorphine, which remains the current treatment of choice for pregnant opioid dependent patients.

Risks of Relapse

Treatment with buprenorphine is also associated with a high risk of relapse (Raistrick et al. 2005), and a remote risk of opioid overdose if the patient uses a significant amount of opioids after losing tolerance. Risk minimization procedures include exclusion of patients with a history of overdose in the past 3 years, regular monitoring of urine toxicology and opioid use, and referral for agonist treatment or inpatient detoxification if relapse occurs.

Blood Tests

Blood drawing may cause slight discomfort at site of needle entry, resulting in a small bruise.

Naloxone Challenge Test

This test will be performed under the supervision of a study physician and will take approximately 45 min to complete. The risks of a dose of 0.2-0.8 mg naloxone administered IM are the signs and symptoms associated with opioid withdrawal ("gooseflesh," "vomiting," "tremor," "uncontrollable yawning," etc.). These will be assessed every 10 min. for up to 45 min. During the procedure, we will measure blood pressure and heart rate before and up to 30 min. after the naloxone dose.

Describe procedures for minimizing risks

Exclusion Criteria: The exclusion criteria of this study are designed to minimize the risks to participants. Patients are excluded if they have severe psychiatric illness (mood disorder with functional impairment or suicide risk, schizophrenia) which might interfere with their ability to participate in the outpatient therapy. A history of recent drug overdoses will be exclusionary. Pregnancy, lactation, or failure to practice a reliable birth control method is exclusionary, and patients are instructed to inform their psychiatrist immediately if they suspect they may be pregnant. Urine HCG is tested during screening and monthly throughout the trial. Serum (quantitative) pregnancy test will be obtained during screening. The baseline medical evaluation includes physical examination, blood chemistry profile (including liver function tests), complete blood count, urinalysis (including HCG), and electrocardiogram, urine toxicology, and naloxone challenge if opiate dependence diagnosis is unclear. The evaluating psychiatrist reviews all these and takes a medical history.

Any disorders which might make buprenorphine-clonidine-naltrexone or naltrexone maintenance hazardous, such as uncontrolled hypertension, diabetes, heart disease, hepatitis with transaminase levels greater than three times the upper limit of normal, renal disease, or advanced AIDS are exclusionary. Participants with uncertain hepatitis status and unexplained liver enzyme elevation > 3 times the upper limit of normal will be offered hepatitis panel testing to determine study eligibility. Patients with acute hepatitis infection and increasing liver function tests during screening will be excluded from study participation. The patient will be assisted in obtaining appropriate medical evaluation and treatment, and may be eligible for the research study once the problem is controlled. History of an allergic reaction to any of the medications used is an exclusion criterion.

Patient Education: All patients will be informed through the informed consent form and discussions with the research psychiatrist and therapist of the possible side effects and risks enumerated above. In addition, at weekly visits the psychiatrist will query side effects in general, and events of specific concern including missing naltrexone doses in conjunction with resumed opiate use or heavy opiate use in an effort to override the blockade, and the risk of overdose and death in these situations. Therapists will also be trained to query for such events and bring them to the attention of the psychiatrist who will follow up. Patients will give informed consent before entering the study. Patients are instructed to call us if any untoward effects occur and are given the phone number of our 24-hour answering service.

Patient Monitoring and Removal from Study: The psychiatrist and/or therapist will assess appropriateness for continuation in the research study on a continuous basis, and will remove from the trial patients with significant clinical deterioration or noncompliance of a type which could be dangerous. If a patient is removed from the research trial for medical reasons, he/she will be retained in open treatment for the remaining of the study period and will be offered a supply of buprenorphine while transitioning to other

treatment. Upon removal of a patient from the trial due to clinical deterioration, the patient will be referred for appropriate follow-up treatment, in most instances either inpatient detoxification or residential treatment, or methadone maintenance. The PI, Co-PI, or a study psychiatrist is available 24 hours/day by phone and/or beeper in case of emergency.

Methods to Protect Confidentiality

Describe methods to protect confidentiality

Patients will be asked to divulge information, such as their drug use or legal, psychiatric or medical problems, which are sensitive and could have adverse social consequences if released. This would include information released to insurance companies, family members, or made public in any way. Patient records are kept in locked files and released only with the patient's signed consent. We will obtain a Federal Certificate of Confidentiality to further safeguard the confidentiality of the participants enrolled in the trial. The Certificate of Confidentiality will allow investigators and others with access to research records to refuse to disclose information that could identify subjects in any civil, criminal, administrative, legislative, or other proceeding, whether at the Federal, State, or local level. Contact with family members or significant others will only be with the patient's express written consent. All computer data are stored without names or other uncoded identification.

Will the study be conducted under a certificate of confidentiality?

Yes, we will apply for the Certificate of Confidentiality

Direct Benefits to Subjects

Direct Benefits to Subjects

Participants may benefit from many of the components of the treatment that they receive, induction onto injection naltrexone, naltrexone maintenance, and components of behavioral therapy.

Compensation and/or Reimbursement

Will compensation or reimbursement for expenses be offered to subjects?

Yes

Please describe and indicate total amount and schedule of payment(s).

Include justification for compensation amounts and indicate if there are bonus payments.

Participants will receive \$40 at each study visit to cover the cost of transportation and time spent completing study related forms. Therefore if a patient attends every study visit, they can earn up to \$1,720.

References

References

Brahen, L. S., Capone, T. J., & Capone, D. M. (1988). Naltrexone: lack of effect on hepatic enzymes. *The Journal of Clinical Pharmacology*, 28(1), 64-70.

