Select the names of persons designated to obtain consent/assent

[name], MD

Type in the name(s) not found in the above list

Study Procedures

Describe the procedures required for this study

Buprenorphine induction/stabilization/taper: Buprenorphine induction will be conducted at the SURC center. After consenting to the study, participants will receive buprenorphine, dispensed weekly, that they will take daily. Participants will be stabilized on, and tapered off, buprenorphine over a 3-week period. Reductions will occur in a graded fashion, with the stabilization dose reduced to 4mg, according to the following schedule:

- **Day 0 (Study Consent + ancillary medications).** Participants will be advised to abstain from opioids for at least 12-16 hours prior to taking their first dose of buprenorphine/naloxone in the clinic the next day.
- **Day 1:** After a COWS of 6-10, participants will receive buprenorphine/naloxone 2/0.5mg. If tolerated, the patient will receive an additional 4mg onsite, with 2mg to take home that evening. Patients will receive a total of 8/2mg on Day 1.
- **Days 2-7:** 8/2 mg buprenorphine/naloxone
- **Days 8-14:** 6/1.5 mg buprenorphine/naloxone
- **Days 15-21:** 4/1 mg buprenorphine/naloxone

Participants will attend the center twice weekly and will be assessed for opioid and other substance use (urine toxicology and self-report), vital signs, opioid withdrawal symptoms, opioid cravings, and dose adjustments of buprenorphine will be made as needed by study physicians. This approach to buprenorphine taper is intended to resemble standard clinical practice, in which patients seeking transition off buprenorphine undergo a slow taper. The purpose is in part to provide a slow transition with minimal withdrawal symptoms. Participants will have at least two study visits a week during the buprenorphine taper, but may be seen more regularly at the center if deemed clinically necessary. Participants will be required to submit at least one opioid negative urine (except for buprenorphine) during the last two weeks of the buprenorphine taper. **Participants who are not able to submit at least one opioid negative urine**

during the last two weeks of the buprenorphine taper will be offered buprenorphine to resume in the clinic and will be provided with referrals.

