Naltrexone induction procedure: Participants who successfully complete the taper must then complete a two-day washout (abstinence from opioids, buprenorphine). During this 48-hour period, participants will report to the center daily for vital sign monitoring and to receive standing doses of ancillary medications (clonidine, clonazepam, zolpidem, prochlorperazine) to alleviate withdrawal and discomfort with additional doses as needed. After abstinence of \geq 48 hours from the last buprenorphine dose, to allow for mu receptor availability, participants will begin the naltrexone induction, using a 3 day ascending taper of oral naltrexone and once the final oral dose of naltrexone 15 mg is tolerated, participants will receive Vivitrol injection.

The administration of naltrexone will occur within a detoxification suite, consisting of a private room outfitted with two comfortable reclining lounge chairs, adjustable lighting, and an entertainment system. Participants will be monitored by clinical staff frequently, with vital signs checks and withdrawal assessments. Transportation home by car service will be provided at the end of the day for any patient deemed to have this clinical need.

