On Day 1 of the naltrexone induction, participants are pre-treated with prochlorperazine, clonidine, and clonazepam, followed by the first dose of naltrexone 1.5mg. If the first dose of naltrexone is tolerated, a second dose of 1.5mg will be administered. Ascending split doses of naltrexone will be titrated up slowly, until the final total dose of 15mg has been given on Day 3 (Day 1: 1.5-3mg, Day 2 : 3-6mg, Day 3: 15mg). Ancillary medications will be offered daily during the induction week and will include clonidine for myalgias, prochlorperazine for nausea, clonazepam to reduce anxiety and dysphoria, and trazodone or zolpidem for insomnia. Participants will be provided take-home doses of ancillary medications in small doses for one week post-administration of Vivitrol. Once a total of 15mg of naltrexone has been tolerated (at least 1.5 hr. observation), the participant may receive 380mg IM Vivitrol. As noted in the section for Procedures for Missed Doses of Vivitrol, if relapse is suspected (the participant reports opioid use, and/or has a positive UDS for opioids) and there is a risk that the participant has developed physical dependence (e.g., delay in receiving scheduled injection or subjective effects suggesting that the block is incomplete) a naloxone challenge will be administered before the participant receives their next injection.

For female participants, a urine pregnancy test will be obtained on the day of Vivitrol administration. If at any time during the study a female participant has a positive urine pregnancy test, this will be reported to the FDA and IRB, the participant will be discontinued from the study, and transitioned to a treatment program in the community.

If a participant is unable to receive Vivitrol on induction Day 3, because they were unable to receive naltrexone due to opioid intoxication or severe withdrawal, the participant will be given up to two additional days to attempt the oral naltrexone titration and Vivitrol induction. **If a patient fails to succeed with the naltrexone initiation procedure, the study team will provide the patient with a weekly supply of buprenorphine, and will be provided with a referral.**

Vivitrol Injections: Vivitrol will be administered as an intramuscular injection (380mg) in one buttock by one of the research psychiatrists or research nurse, who are currently trained and administer Vivitrol in other

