Participants will receive counseling focused on medication adherence, education about management of withdrawal symptoms, on correct medication usage and the importance of adherence to study procedures and abstinence from any substance use outside of the protocol. All participants will receive behavioral therapy once weekly during the stabilization and post-induction phase, and daily (Mon-Fri) during the naltrexone induction phase. Physician will meet with participants during each visit during the induction process and weekly during the buprenorphine stabilization, and post-induction phases. The goals of these counseling sessions are to: educate and support the patient as he or she stabilizes on XR-NTX, provide a motivational platform to discuss pharmacological and nonpharmacological strategies for the management of opioid withdrawal symptoms, provide education regarding any medication side effects, and increase patient's motivation to adhere to the XR-naltrexone and to remain on it with the provider in the community after the completion of the study.

Buprenorphine/naloxone will be offered to participants if they relapse to opioids or if they are unable to tolerate study procedures at any point in the study, as well as at the end of study if they no longer wish to continue treatment with Vivitrol.

You can upload charts or diagrams if any

Criteria for Early Discontinuation

Criteria for Early Discontinuation

- 1) Development of serious psychiatric symptoms as indicated by the Clinical Global Impression (CGI) improvement score of 6 (much worse than baseline) or greater for 2 consecutive weeks.
- 2) If the participant's continued opioid use places him/her at risk for self-destructive behavior or other harm as indicated by a CGI improvement score of 6 or more (much worse than baseline) for 2 consecutive weeks, or as determined by clinical judgement .
- 3) Development of serious medical condition(s) that may or may not be related to study participation as assessed by weekly visits with the psychiatrist, vital sign measurements, and weekly urine toxicology.
- 4) If the participant becomes pregnant as assessed by monthly urine pregnancy testing.

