Participants may be also removed from the trial if they repeatedly miss scheduled appointments or clinical worsening necessitates more intensive treatment (drop out criteria are defined above). Subjects who develop serious psychiatric symptomatology (e.g. psychosis, suicidal ideation, severe depressive symptoms) during the study period will be dropped from the study and appropriate clinical referrals will be made. This would include, but not be limited to, patients who become unconscious after using, engage in destructive or violent behavior while intoxicated, report driving while intoxicated, or develop medical complications from their opioid use. In all cases where subjects are discontinued from the study, the clinical research staff will assume clinical responsibility for the subjects until clinical referrals are operational.

In the case that the patient is removed from the research trial for medical reasons, or is requesting withdrawal from the study, he/she will be retained in open treatment for the remaining study period. Upon removal of a patient from the trial due to clinical deterioration, the patient will be referred for appropriate follow-up treatment, in the most instances either intensive outpatient or residential treatment. The PI or a study psychiatrist is available 24 hours/day by phone and/or beeper in case of emergency.

If a patient is discontinued from the study, or decides to withdraw, or relapses during study participation, the patient will get treated with buprenorphine until they are linked with a referral for continuing buprenorphine treatment. Participants will receive a one-week supply of buprenorphine at a time during the transition process.

Buprenorphine will be also offered to participants if they are unable to continue with Vivitrol treatment at the end of the study. If additional injections of Vivitrol are available, they will also be offered to patients at the end of the treatment study.

Blood and other Biological Samples

Please create or insert a table describing the proposed collection of blood or other biological specimens. Urine samples will be collected at every visit, and we will use onsite testing to provide immediate feedback on opiate use to the participant and the treatment team. Blood chemistry will be obtained at baseline and end of study. Urine pregnancy tests will be obtained at baseline and prior to each administration of XR-NTX.

Assessment Instruments

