Discontinuation of buprenorphine is associated with opioid withdrawal symptoms ranging from mild-moderate to more severe reactions. Study physicians have extensive experience, in both research and clinical settings, in administering buprenorphine and in the management of opioid withdrawal symptoms. The use of buprenorphine is also associated with the risk of using the medication for the purposes of intoxication. In the present study we will use buprenorphine/naloxone combination product, which has lower abuse liability. If sublingual buprenorphine is used parenterally, there is a risk of precipitated opioid withdrawal. Such an event, if it were to occur, would be short-lived and not life threatening. Participants will be warned of this risk and advised not to use the medication in this manner. If it is determined that patients have been abusing their buprenorphine in such a manner, they will be declared to have failed BUP discontinuation, and a new treatment plan will be developed by the patient's clinical team, with possibilities including transfer to buprenorphine or methadone maintenance. To minimize the risk of diversion,

medication will be dispensed for short time intervals (1-2 weeks of medication at a time).

Buprenorphine is metabolized principally by CYP3A4. Co-administration of other CYP3A4 inhibitors (e.g. anti-- retrovirals efavirenz, delavirdine, atazanavir or atazanavir/ritonavir; the anti-fungal agent ketoconazole;; antibiotics erythromycin or clarithromycin) may cause an increase in systemic levels of buprenorphine, although this does not usually have clinically significant effects. When a patient being prescribed buprenorphine is also receiving other medications, the prescribing physician will check for potential interactions ahead of time and monitor during treatment.

Side Effects of Extended--Release (XR), Injectable Naltrexone

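### The pregnancy-test rules do not guarantee a repeat test before the first oral naltrexone dose; one added urine test would close this small gap

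*Protocol*

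**What the plan says.** The protocol has four kinds of pregnancy-test rule.

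- **Screening or baseline.** Pregnancy is an exclusion, checked by urine and serum tests (Inclusion/Exclusion Criteria; Pregnancy, under Risks).
- **Injection-linked.** Study Procedures, Naltrexone induction procedure: "For female participants, a urine pregnancy test will be obtained on the day of Vivitrol administration". Blood and other Biological Samples: "Urine pregnancy tests will be obtained at baseline and prior to each administration of XR-NTX".
- **Monthly.** Procedures for minimizing risks: "Urine HCG is tested during screening and monthly throughout the trial". One of the Criteria for Early Discontinuation reads: "If the participant becomes pregnant as assessed by monthly urine pregnancy testing". Neither place gives a start date or a window.
- **As needed.** The Pregnancy paragraph under Risks adds urine testing during treatment on clinical indication.

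The drug schedule is in Study Procedures. The last scheduled buprenorphine dose is on Day 21. After an interval of at least "48 hours from the last buprenorphine dose, to allow for mu receptor availability, participants will begin the naltrexone induction". Oral naltrexone rises over three days to 15 mg, with up to two more days allowed, and the injection follows. The steps listed before the first 1.5 mg dose are pre-treatment with three ancillary drugs; a pregnancy test is not among them. The SAP does not mention pregnancy testing.

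**The concern.** The protocol asks for a fresh test before each injection, but the step meant to precipitate withdrawal is the oral naltrexone that comes first (Risks of the Rapid Naltrexone Induction Procedure). The Pregnancy paragraph says that a woman who becomes pregnant leaves study medication and is offered methadone or buprenorphine. The timing of a positive result therefore matters in two ways.

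- **Before the final buprenorphine dose:** she can simply stay on buprenorphine. This is the larger benefit, because stopping it has consequences of its own: "Discontinuation of buprenorphine is associated with opioid withdrawal symptoms ranging from mild-moderate to more severe reactions".
- **After that dose but before oral naltrexone:** she is spared only the added, precipitated withdrawal.

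If the first repeat result comes on the day of injection, both opportunities have passed. A woman who starts oral naltrexone and is never injected does not reach the injection-linked test at all.

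**Working it through.** No figure in the plan bears on this point, so the check is calendar arithmetic on the nominal schedule.

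**Inputs**
- Last buprenorphine dose: Day 21 (Study Procedures).
- Washout: at least 48 hours, also described as two days (same section).
- Injection: induction Day 3, or up to Day 5 with the two extra days (same section).
- Lag L from screening test to Day 0: assumed 0-14 days. The range comes from the possible delay of up to two weeks under Research Related Delay to Treatment; no test-to-consent interval is stated.
- Length of a month M: assumed 28-31 days.

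**Step 1. First oral dose, D.** 21 + 2 = Day 23 (exactly 48 hours), or 21 + 3 = Day 24 (two full washout days).

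**Step 2. Injection-linked test.** D + 2 to D + 4, which is Day 25-26, or Day 27-28 if titration is extended. This is 2-4 days after the first oral dose.

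**Step 3. Monthly test counted from screening.** It falls on Day M - L. It is in time, counting a test on the same day before dosing, if M - L ≤ D, that is, if L ≥ M - D.

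| M (days) | Lag needed, D = 24 | Lag needed, D = 23 |
|---|---|---|
| 28 | 4 | 5 |
| 30 | 6 | 7 |
| 31 | 7 | 8 |

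The threshold is thus about 4-8 days. Women with a shorter lag are not covered.

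**Step 4. Monthly test counted from Day 0.** It falls on Day 28-31. The distance from D is 28 - 24 = 4 to 31 - 23 = 8 days after the first oral dose, so nobody is covered in time.

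**Step 5. Age of the last certain test at the first oral dose, D + L.**
- L = 0: 23-24 days.
- L = 14: 37-38 days, but only if the monthly clock does not start at screening. If it does, a retest has already fallen on Day 14-17 (28 - 14 to 31 - 14).
- Clock starting at screening: a woman who is not retested in time has L of at most M - D - 1, so her last test is at most M - 1 = 27-30 days old.

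**Step 6. With one added test.** At the last taper visit, assumed to fall on Day 18-21, the result is 23 - 21 = 2 to 24 - 18 = 6 days old at the first oral dose. In washout or just before dosing it is 0-2 days old.

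**Step 7. Number of women.** The expected sample is 75% male, so 25% × 45 = 11.25, or about 11 women enrolled. Fewer will reach oral naltrexone, because some will leave during the taper.

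**The case against.** The case for leaving the plan alone is a fair one.

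- The monthly rule names screening first, so screening is its natural starting point. Final consent follows a full psychiatric and medical workup, so a lag of zero is probably not typical. Many women may be retested in time. This stands, and it is why the point is about a guarantee and not about an absent test.
- Safeguards already exist: serum and urine tests at entry, required contraception, an instruction to report suspected pregnancy at once, and a low starting dose (1.5-6 mg over induction Days 1-2). This stands and keeps the risk small.
- A woman who fails induction returns to a suitable drug anyway: "If a patient fails to succeed with the naltrexone initiation procedure, the study team will provide the patient with a weekly supply of buprenorphine". That largely answers the worry about her onward treatment, but not about the withdrawal she has already gone through.
- A test just before oral naltrexone comes too late to keep a woman on buprenorphine without a break. This is correct, and it is why the last taper visit is the better time.

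A reader might also infer more than the documents support. The rules do not contradict one another: they are cumulative, and staff can follow all of them at once. Vivitrol is not given untested, since two separate sections require a test at each injection. Nor do the monthly rule or the sentence on clinically indicated tests need rewriting. Monthly testing already runs throughout the trial, and no defect in either rule has been shown.

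**Conclusion.** The gap is real but minor. No rule, and no combination of rules, ensures a repeat pregnancy test before the first oral naltrexone dose at about Day 23-24. Whether a given woman has one depends on an unstated monthly starting point and on her screening lag. The injection-linked test comes 2-4 days later.

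This rests on the nominal schedule, a month of 28-31 days, and an assumed lag of 0-14 days. The documents give no pregnancy rate, so I do not put a number on expected cases; with at most about 11 women and a few weeks of exposure, the absolute risk is small. This is an inexpensive safety improvement. It is not a design flaw, and it does not affect the primary endpoint, the analysis or the sample size.

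**What to change.** Add one sentence to Study Procedures, Naltrexone induction procedure, and the same item to the list in Blood and other Biological Samples. Suggested wording:

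*Women must have a negative urine pregnancy test before naltrexone induction, preferably at the last taper visit before the final buprenorphine dose, and in every case before the first oral naltrexone dose.*

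Leave all other pregnancy-test rules as they are.

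The cost is a short amendment and about one test strip per woman, for at most about 11 women. No new visit or sample is needed: "Participants will have at least two study visits a week during the buprenorphine taper", attendance is daily during washout, and urine is already collected at every visit.
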